10.13. Appendix 13: Provisions for Changes in Study Conduct During Exceptional Circumstances

Implementation of this appendix

The changes to procedures described in this appendix are temporary measures intended to be used only during specific time periods as directed by the sponsor in partnership with the investigator.

Exceptional circumstances

Exceptional circumstances are rare events that may cause disruptions to the conduct of the study. Examples include pandemics or natural disasters. These disruptions may limit the ability of the investigators, participants, or both to attend on-site visits or to conduct planned study procedures.

Implementing changes under exceptional circumstances

In an exceptional circumstance, after receiving the sponsor's written approval, sites may implement changes if permitted by local regulations.

Ethical Review Boards (ERBs), regulatory bodies and any other relevant local authorities, as required, will be notified as early as possible to communicate implementation of changes in study conduct due to exceptional circumstances. To protect the safety of study participants, urgent changes may be implemented before such communications are made, but all changes will be reported as soon as possible following implementation. If approval of ERBs, regulatory bodies, or both is required per local regulations, confirmation of this approval will be retained in the study records.

In the event written approval is granted by the sponsor for changes in study conduct, additional written guidance, if needed, will be provided by the sponsor.

Considerations for making a change

The prevailing consideration for making a change is ensuring the safety of study participants. Additional important considerations for making a change are

- Good Clinical Practice compliance, and
- minimization of risk to study integrity.

Such changes are intended to

- mitigate risks of participants missing visits
- allow participants to continue safely in the study, and
- maintain the data integrity of the study.

Informed Consent

Additional consent from the participant will be obtained, as applicable, for

- participation in remote visits (as defined in the “Changes in Study Conduct” section below)
- a change in the method, location, or both, of study intervention administration,
- dispensation of additional study drug during an extended treatment period
- alternate delivery of study intervention and ancillary supplies, and,

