- provision of their personal or medical information required prior to implementation of these activities.

Changes in Study Conduct

Changes in study conduct not described in this appendix, or not consistent with applicable local regulations, are not allowed.

The following changes in study conduct will not be considered protocol deviations. Missing data will be captured as protocol deviations.

1. Remote visits and adjustments to visit interval tolerance

Whenever possible and safe to do so, as determined by the investigator’s discretion, participants should complete the usual SoA. To maximize the possibility that the study visits can be conducted as on-site visits, the visit interval tolerances (visit windows) may be adjusted within the ranges specified in the following table. This minimizes missing data and preserves the intended conduct of the study.

The table also shows the acceptable location types for various study visits. Remote options described in the sponsor’s guidance and written approval may include: a) telephone, IT-assisted virtual, or both; b) mobile healthcare; and c) other. More information on these options follows the table.

Screening and Induction Period (SOA Table 1)		
For this visit...	Permitted Visit Types	Visit Interval Tolerance^a
Visit 1	on-site only	same as shown in SOA, but flexibility can be considered following consultation with, and with prior approval by, the sponsor
Visit 2	on-site only	same as shown in the SOA
Visit 3 through Visit 8	remote	same as shown in the SOA
Visit 9	remote	for endoscopy : 3 days before to 28 days after the targeted visit date (inclusive) for other procedures : same as shown in the SOA
Maintenance Treatment Period (SOA Table 2)		
Visit 10 through Visit 28	remote	same as shown in the SOA
Visit 29	remote	for endoscopy : from 3 days before to 56 days after the targeted visit date (inclusive) for other procedures : same as shown in the SOA
Extension Induction and Extension Maintenance Treatment Periods (SOA Table 3)		
Visit 10 through Visit 15	remote	same as shown in the SOA

Visit 16	remote	for endoscopy : from 3 days before to 28 days after the targeted visit date (inclusive) for other procedures : same as shown in the SOA
Visit 17 through Visit 28	remote	same as shown in the SOA
Visit 29	remote	for endoscopy : from 3 days before to 56 days after the targeted visit date (inclusive) for other procedures : same as shown in the SOA

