2. Local laboratory testing option

Local laboratory testing may be conducted in lieu of central laboratory testing. However, central laboratory testing must be retained for the following samples: **CCI** PK,

CCI flow cytometry panel, genetics sample, tests of CCI, and tests obtained because of a systemic hypersensitivity event. The local laboratory must be qualified in accordance with applicable local regulations.

3. Investigational product and ancillary supplies (including participant diaries)

When a participant is unable to go to the site to receive study supplies during normal on-site visits, the site should work with the sponsor to determine appropriate actions. These actions may include

- asking the participant to go to the site and receive study supplies from site staff without completion of a full study visit
- asking the participant's designee to go to the site and receive study supplies on a participant's behalf,
- arranging delivery of study supplies, and
- working with the sponsor to determine how study intervention is to be administered to the participant, for example, administration of study drug to the participant during a mobile healthcare visit or at an alternate location.

These requirements must be met before action is taken:

- Alternate delivery of IP should be performed in a manner that does not compromise treatment blinding and ensures product integrity. The existing protocol requirements for product accountability remain unchanged, including verification of participant's receipt of study supplies.
- When delivering supplies to a location other than the study site (for example, participant's home), investigator, sponsor, or both should ensure oversight of the shipping process to ensure accountability and product quality (that is, storage conditions maintained and intact packaging upon receipt).
- Instructions may be provided to the participant or designee on the final disposition of any used or unused study supplies.

In addition, if study intervention is to be administered to the participant during a mobile healthcare visit or at an alternate location, this additional requirement must be met: only personnel authorized by the primary investigator or by the sponsor may supply or administer study intervention.

Missing Endoscopies

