During exceptional circumstances, some sites might not be able to conduct endoscopies. Gastrointestinal societies have recommended that patients with IBD who do not have COVID-19 should stay on IBD therapies with a goal of sustaining remission.^{33,34} For participants in a clinical study, remaining on an assigned study treatment might be protective against immediate risk of disease worsening or recurrence. Remaining on study treatment might also alleviate stress

for the participant, the healthcare provider, and the medical system insofar as stress is created by withdrawing participants study treatment and then needing to find alternative therapies for the withdrawn participants.

This section of this appendix addresses the retention of participants in the study who, in the opinion of the investigator, could benefit from continuing to receive study treatment, despite their inability to have certain protocol-specified endoscopies. Such participants are referred to herein as “Impacted Patients.”

A determination of clinical response status, as described in Section 8.1 of the protocol, relies upon stool frequency and rectal bleeding data. Therefore, if a participant is found to be noncompliant with their daily diary entry to the extent that an assessment of clinical response status cannot be made, the participant will not be eligible to be regarded as an Impacted Patient.

The investigator or designee must notify the sponsor and make a request to classify a participant as an “Impacted Patient.” However, before doing so, the options for extended visit interval tolerances (wider windows) should be exhausted. Also, other options to enable performing the endoscopy within the allowed timing should be considered, for example, use of an alternate, approved endoscopy site. If, after considering these options, an endoscopy must nevertheless be missed, the investigator or designee must describe in the Impacted Patient’s source documents both the reason for the missed endoscopy and the options which were considered but rejected.

Without data from postbaseline endoscopies, it is not possible to use per protocol criteria to determine the participant’s status as a responder or nonresponder at the end of the Induction Period or to determine a participant’s response to Extension Induction or Extension Maintenance dosing, or to determine clinical response/remission status at Week 52.

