6.6. Appendix 6: Daily Diary Calculations

Weekly summary measures of daily diary data will be created for each patient. The 7-day period associated with each week will be defined using a visit centric approach. The table below displays the interval for each week:

Week (Visit)	Start Day ^a	End Day ^a
Baseline	Week 0 Visit Date – 7	Week 0 Visit Date – 1
Week 1 (V3)	Max(Week 0 Visit Date, Week 1 Visit Date – 7)	Week 1 Visit Date – 1
Week 2 (V4)	Max(Week 1 Visit Date , Week 2 Visit Date – 7)	Week 2 Visit Date – 1

Week 3	Max (Week 2 Visit Date, Week 4 Visit Date – 14)	Week 4 Visit Date – 8
Week 4 (V5)	Max (Week 2 Visit Date, Week 4 Visit Date – 7)	Week 4 Visit Date – 1
Week 5	Max (Week 4 Visit Date, Week 6 Visit Date – 14)	Week 6 Visit Date – 8
Week 6 (V6)	Max (Week 4 Visit Date, Week 6 Visit Date – 7)	Week 6 Visit Date – 1
Week 7	Max (Week 6 Visit Date, Week 8 Visit Date – 14)	Week 8 Visit Date – 8
Week 8 (V7)	Max (Week 6 Visit Date, Week 8 Visit Date – 7)	Week 8 Visit Date – 1
Week 9	Max (Week 8 Visit Date, Week 10 Visit Date – 14)	Week 10 Visit Date – 8
Week 10 (V8)	Max (Week 8 Visit Date, Week 10 Visit Date – 7)	Week 10 Visit Date – 1
Week 11	Max (Week 10 Visit Date, Week 12 Visit Date – 14)	Week 12 Visit Date – 8
Week 12 (V9)	Max (Week 10 Visit Date, Week 12 Visit Date – 7)	Week 12 Visit Date – 1
Week 13	Max (Week 12 Visit Date, Week 14 Visit Date – 14)	Week 14 Visit Date – 8
Week 14 (V10)	Max (Week 12 Visit Date, Week 14 Visit Date – 7)	Week 14 Visit Date – 1
Week 15	Max (Week 14 Visit Date, Week 16 Visit Date – 14)	Week 16 Visit Date – 8
Week 16 (V11)	Max (Week 14 Visit Date, Week 16 Visit Date – 7)	Week 16 Visit Date – 1
Week 17	Max (Week 16 Visit Date, Week 18 Visit Date – 14)	Week 18 Visit Date – 8
Week 18 (V12)	Max (Week 16 Visit Date, Week 18 Visit Date – 7)	Week 18 Visit Date – 1
Week 19	Max (Week 18 Visit Date, Week 20 Visit Date – 14)	Week 20 Visit Date – 8
Week 20 (V13)	Max (Week 18 Visit Date, Week 20 Visit Date – 7)	Week 20 Visit Date – 1
Week 21	Max (Week 20 Visit Date, Week 22 Visit Date – 14)	Week 22 Visit Date – 8
Week 22 (V14)	Max (Week 20 Visit Date, Week 22 Visit Date – 7)	Week 22 Visit Date – 1
Week 23	Max (Week 22 Visit Date, Week 24 Visit Date – 14)	Week 24 Visit Date – 8
Week 24 (V15)	Max (Week 22 Visit Date, Week 24 Visit Date – 7)	Week 24 Visit Date – 1
Week 25	Max (Week 24 Visit Date, Week 26 Visit Date – 14)	Week 26 Visit Date – 8
Week 26 (V16)	Max (Week 24 Visit Date, Week 26 Visit Date – 7)	Week 26 Visit Date – 1

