Week 27	Max(Week 26 Visit Date, Week 28 Visit Date – 14)	Week 28 Visit Date – 1
Week 28 (V17)	Max(Week 26 Visit Date , Week 28 Visit Date – 7)	Week 28 Visit Date – 1

Week 29	Max (Week 28 Visit Date, Week 30 Visit Date – 14)	Week 30 Visit Date – 8
Week 30 (V18)	Max (Week 28 Visit Date, Week 30 Visit Date – 7)	Week 30 Visit Date – 1
Week 31	Max (Week 30 Visit Date, Week 32 Visit Date – 14)	Week 32 Visit Date – 8
Week 32 (V19)	Max (Week 30 Visit Date, Week 32 Visit Date – 7)	Week 32 Visit Date – 1
Week 33	Max (Week 32 Visit Date, Week 34 Visit Date – 14)	Week 34 Visit Date – 8
Week 34 (V20)	Max (Week 32 Visit Date, Week 34 Visit Date – 7)	Week 34 Visit Date – 1
Week 35	Max (Week 34 Visit Date, Week 36 Visit Date – 14)	Week 36 Visit Date – 8
Week 36 (V21)	Max (Week 34 Visit Date, Week 36 Visit Date – 7)	Week 36 Visit Date – 1
Week 37	Max (Week 36 Visit Date, Week 38 Visit Date – 14)	Week 38 Visit Date – 8
Week 38 (V22)	Max (Week 36 Visit Date, Week 38 Visit Date – 7)	Week 38 Visit Date – 1
Week 39	Max (Week 38 Visit Date, Week 40 Visit Date – 14)	Week 40 Visit Date – 8
Week 40 (V23)	Max (Week 38 Visit Date, Week 40 Visit Date – 7)	Week 40 Visit Date – 1
Week 41	Max (Week 40 Visit Date, Week 42 Visit Date – 14)	Week 42 Visit Date – 8
Week 42 (V24)	Max (Week 40 Visit Date, Week 42 Visit Date – 7)	Week 42 Visit Date – 1
Week 43	Max (Week 42 Visit Date, Week 44 Visit Date – 14)	Week 44 Visit Date – 8
Week 44 (V25)	Max (Week 42 Visit Date, Week 44 Visit Date – 7)	Week 44 Visit Date – 1
Week 45	Max (Week 44 Visit Date, Week 46 Visit Date – 14)	Week 46 Visit Date – 8
Week 46 (V26)	Max (Week 44 Visit Date, Week 46 Visit Date – 7)	Week 46 Visit Date – 1
Week 47	Max (Week 46 Visit Date, Week 48 Visit Date – 14)	Week 48 Visit Date – 8
Week 48 (V27)	Max (Week 46 Visit Date, Week 48 Visit Date – 7)	Week 48 Visit Date – 1
Week 49	Max (Week 48 Visit Date, Week 50 Visit Date – 14)	Week 50 Visit Date – 8
Week 50 (V28)	Max (Week 48 Visit Date, Week 50 Visit Date – 7)	Week 50 Visit Date – 1
Week 51	Max (Week 50 Visit Date, Week 52 Visit Date – 14)	Week 52 Visit Date – 8
Week 52 (V29)	Max (Week 50 Visit Date, Week 52 Visit Date – 7)	Week 52 Visit Date – 1

Abbreviations: V = Visit.

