^a If End Day < Start Day, do not assign specified visit week. Visit date will be calculated by selecting the first date from the following list (i.e., first in list order): (1) date of earliest bowel preparation if bowel preparation date is available, (2) date of endoscopy if endoscopy was performed, (3) date of treatment if treatment was given, (4) office visit date if available, or (5) imputed date of visit center of the protocol-defined window for that visit. The screening endoscopy is assumed to be associated with the Week 0 visit.

For the Mayo SF and RB subscores, the most recent 3 nonmissing days of the 7-day period in the table above will be averaged and rounded to the nearest integer to calculate the weekly score for each patient. Patients with less than 3 measurements in the 7 day period will be considered missing.

For the Bristol Stool Scale the worst (i.e. maximum) of the available measures during the 7 period in the table above will be used to calculate a weekly score for each patient. If fewer than 4 days are available (i.e., not missing), the patient will be considered to be missing data for that week.

For all other daily diary measures, all available days of the 7 days will be averaged and rounded to the nearest integer to calculate the weekly score for each patient. If fewer than 4 days are available (i.e., not missing), the patient will be considered to be missing data for that week.

If multiple diary assessments on a single day are present, use the earliest nonmissing assessment. Data from the following days will be considered missing: (i) days when patients receive bowel preparation, (ii) the day of an endoscopy, and (iii) two days after an endoscopy.

If the baseline assessment is missing per the above rules, the first available postbaseline assessment starting with Week 1 will be used to impute the baseline so that the patient can be included in the analysis.

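### A late Week 52 endoscopy under the exceptional-circumstances rules can make two symptomatic endpoints fail, or be read up to 56 days late, although neither uses endoscopy

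*Protocol*

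**What the plan says.** **Protocol 10.13 (Appendix 13).** The Visit 29 row widens the window for endoscopy only, "from 3 days before to 56 days after the targeted visit date (inclusive"). Other Visit 29 procedures keep the schedule's tolerance. Table 2 and Table 3 put Visit 29 at Day 365 ±3 and list diary return there. Before a site may ask for Impacted Patient status for a missed endoscopy, "the options for extended visit interval tolerances (wider windows) should be exhausted".

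**SAP 6.6.** The Week 52 diary period starts at "Max (Week 50 Visit Date, Week 52 Visit Date – 7") and ends the day before the Week 52 visit date. That visit date is the first available item in a list:
1. "date of earliest bowel preparation if bowel preparation date is available";
2. endoscopy date;
3. treatment date;
4. office visit date;
5. an imputed date.

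Stool frequency (SF) and rectal bleeding (RB) need at least 3 days in the period. The other diary measures need 4.

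**SAP 4.1.2.1.** A participant without an adequate Week 52 assessment is a non-responder.

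**SAP Table KFAH.3.** Symptomatic remission and symptomatic response are defined by SF and RB alone. SAP 4.4.1.3 limits the Week 52 binary endpoints to Week 12 responders.

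**The concern.** The appendix lets the endoscopy move by up to eight weeks but leaves the diary return where it was. The SAP then ties every Week 52 diary score to the procedure that moved. A participant can complete the diary for the whole scheduled Week 52 period, return it on time, have the endoscopy inside the permitted window, and still have no usable SF or RB score.

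That matters most for the two symptomatic endpoints, because the timing of an endoscopy they do not use would decide them. The ordering is also odd. If the Visit 29 endoscopy is missed altogether and no preparation is taken, items 1 and 2 of the date list are empty, and item 3 is empty because there is no dosing at Visit 29. The anchor becomes the office visit, and the scheduled week counts. The participant who has the endoscopy late, by the route the appendix asks sites to try first, is the one whose scheduled week is discarded.

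**Working it through.** **Inputs from the documents.** Week 50 visit at Day 351, Visit 29 target Day 365, diary return Day 362–368, endoscopy up to Day 421 (365 + 56), minimum 3 days for SF/RB and 4 for the other diary measures.

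**Assumptions, not given in the documents.** Preparation starts on the day of endoscopy or the day before. The last diary entry L is made on the return day or the day before it. All entries up to L are present.

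**On-target check.** Let P be the preparation day, or the endoscopy day if there is no preparation date. The window is [max(351, P − 7), P − 1]. With P = 365 it is Days 358–364; with P = 364 it is Days 357–363. Both give the SAP's 7-day period.

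**Diary returned on schedule.** For a late endoscopy the usable days run from P − 7 to L, so their number is L − P + 8. At least 3 days requires P ≤ L + 5.

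| Return day | Last entry L | Last P with 3 days | Last endoscopy day, preparation same day | Last endoscopy day, preparation the day before |
|---|---|---|---|---|
| 362 | 361 | 366 | +1 | +2 |
| 365 | 364 | 369 | +4 | +5 |
| 365 | 365 | 370 | +5 | +6 |
| 368 | 367 | 372 | +7 | +8 |
| 368 | 368 | 373 | +8 | +9 |

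Days 358–364 can be complete only if L ≥ 364. The cut-off for complete diaries is therefore +4 to +9, and +4 to +6 for return on Day 365. With L = 364 and same-day preparation, an endoscopy at +5 has the window Days 363–369, which holds 2 entries. At +9 the window is Days 367–373, which holds none. A 2-day preparation lead would move the upper end to +10.

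The other diary measures need P ≤ L + 4, one day earlier throughout: +3 to +8 with complete diaries, and +3 to +5 for return on Day 365.

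**Endpoints reached.** Four of the 8 Week 52 binary endpoints use SF and RB: clinical remission, clinical response, symptomatic remission and symptomatic response. All four become non-response. Six of the 7 PROs come from the diary (all but IBDQ); they are missing at Week 52 and left to the MMRM. The endoscopic and histologic endpoints are read late but are not forced to fail.

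**Diary kept until the endoscopy.** Seven days are always available, so nothing is missing. But with P = 421 the window is Days 414–420, a shift of 421 − 365 = 56 days. From P = 372 the window starts at Day 365, and none of Days 358–364 counts towards Week 52.

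**Check of the proposed rule.** Anchored on the office visit at return day R, the window R − 7 to R − 1 holds 7 diary days. Anchored on the imputed Day 365, it holds 4 to 7, since L is at least 361. Both minimums are met whenever the entries were made.

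**The case against.** **The diary would probably be kept.** The table's footnote foresees extra study drug for extended windows, and the consent list mentions an extended treatment period. The supplies section is headed "Investigational product and ancillary supplies (including participant diaries"), and the appendix says that "additional written guidance, if needed, will be provided by the sponsor". Visit 29 may be remote, so the device may not come back on schedule, and the modified Mayo review at that visit gives sites a reason to keep it running. This makes keeping the diary plausible, but it does not settle the matter. The footnote concerns drug, the supplies section concerns receiving materials, and guidance is conditional. A reader might go further and infer from "Changes in study conduct not described in this appendix, or not consistent with applicable local regulations, are not allowed" that keeping the diary is forbidden. The text does not go that far: it neither requires nor expressly bars it. Keeping the diary also only exchanges missing scores for late ones.

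**The endoscopy anchor is deliberate.** Pairing SF and RB with the endoscopy is sound for clinical remission and clinical response, and Inclusion Criterion 6 uses the same pairing. That stands, and the fix leaves it alone. It does not justify the anchor for measures without an endoscopic component.

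**The reach is small.** This stands. The appendix covers rare events and needs the sponsor's written approval. The binary endpoints concern Week 12 responders only, and these are secondary endpoints tested without multiplicity adjustment.

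**Conclusion.** The point holds as a minor one. Read literally, the two documents make symptomatic remission and symptomatic response fail at Week 52 once the endoscopy is later than about +4 to +9 days after target, despite complete diaries for Days 358–364. If the diary is kept, those endpoints and the diary PROs are read up to 56 days late. The range rests on the assumed 0–1 day preparation lead and on whether an entry is made on the return day.

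Four stronger readings are not supported:
- **That loss begins at +1 with a complete diary.** The +1 to +3 end needs a last entry before Day 364, so Days 358–364 are then incomplete.
- **That most participants are exposed.** Under every 0–1 day lead the score is lost from +10 to +56, which is 47 of the 60 allowed days. Those are calendar days, not participants, and the documents give no frequency of late endoscopies.
- **That the arms are affected differently.** Nothing in the documents shows this.
- **That the Week 12 primary endpoint shares the problem.** The Week 12 row has the same form, "Max (Week 10 Visit Date, Week 12 Visit Date – 7"), but the diary stays in use after Visit 9, so SF and RB are not lost this way.

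**What to change.** 1. **Appendix 13:** state that if the Visit 29 endoscopy is delayed, the participant keeps the diary and continues daily entries until it is done.
2. **SAP 6.6:** state that if the Visit 29 endoscopy is done after the Visit 29 visit, Week 52 symptomatic remission, symptomatic response and diary PROs use the 7 days before the Visit 29 date (office visit date, else the imputed date).
3. **Clinical remission and clinical response:** keep the preparation/endoscopy anchor with non-responder imputation as the main rule. Add one sensitivity analysis that uses the scheduled Visit 29 diary week when fewer than 3 days precede the late endoscopy. Report by arm the number of Visit 29 endoscopies after Day 368.

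The cost is one sentence in the appendix, a short addition to SAP 6.6, one sensitivity run and one count by arm. The downside is that in a few participants the composite and symptomatic endpoints may use different diary weeks, so someone could be in clinical remission without being in symptomatic remission. Setting the rule before unblinding avoids choosing the diary week afterwards.
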